# 7.1.1 General Methods: Efficacy

#### **Protection of Type I Error**

Family-wise Type I error will be protected in the strong sense across all primary and secondary endpoints. The p-values from sensitivity analyses for efficacy endpoints are for descriptive purpose only and not adjusted for multiplicity.

#### **Stratification Factors**

For all stratified analyses, stratification factors will be based on the randomization factors (Section 2.2). Specifically, stratification factors used for analyses are as follows:

- for Subjects Expressing PD-L1:
  - region (J/K/T vs rest of Asia vs. RoW)
  - ECOG performance status (0 vs. 1)
  - number of organs with metastases ( $\leq 1 \text{ vs.} \geq 2$ )
- for All Randomized Subjects
  - region (J/K/T vs. rest of Asia vs. RoW)
  - ECOG performance status (0 vs. 1)
  - number of organs with metastases ( $\leq 1 \text{ vs.} \geq 2$ )
  - PD-L1 expression level (≥ 1% vs. < 1% or indeterminate)

Unless otherwise specified, stratification factors are used as entered in the IRT.

In the situation that the stratification factors are adjusted as specified per Section 7.1 General Methods, the adjustment will apply to all the stratified analyses in this document.

#### **General Methods for Time-to-event Variables**

Time to event distribution (e.g. OS, PFS, DOR) will be estimated using Kaplan-Meier (KM) techniques.

Median survival time along with 95% or adjusted confidence interval (CI) will be constructed based on a log-log transformed CI for the survivor function  $S(t)^8$ , Rates at fixed timepoints (e.g. OS at 6 months) will be derived from the KM estimate and corresponding CI will be derived based on Greenwood formula  for variance derivation and on log-log transformation applied on the survivor function  $S(t)^{11}$ .

Unless otherwise specified, the stratified log-rank test will be performed to test the comparison between time to event distributions. Unless otherwise specified, the stratified HR between

2 treatment groups along with CI will be obtained by fitting a stratified Cox model with the treatment group variable as unique covariate.

# **General Methods for Bivariate Variables**

The difference in rates between the two treatment arms along with their two-sided 95% CI will be estimated using the following Cochran-Mantel-Haenszel (CMH) method of weighting , adjusting for the stratification factors:

$$\hat{\theta} = \frac{\sum_{i} w_{i} \hat{\theta}_{i}}{\sum_{i} w_{i}} \sim N \left[ \theta, \frac{\sum_{i} w_{i}^{2} \left[ \frac{p_{ix}(1 - p_{ix})}{n_{ix} - 1} + \frac{p_{iy}(1 - p_{iy})}{n_{iy} - 1} \right]}{\left(\sum_{i} w_{i}\right)^{2}} \right]$$

where  $\hat{\theta} = p_{ix} - p_{iy}$  is the rate difference of the ith stratum,  $w_i = \frac{n_{ix}n_{iy}}{n_{ix} + n_{iy}}$ , and  $n_{ix}$  and  $n_{iy}$  are the number of subjects randomized to treatments x and y, respectively, in the ith stratum. Associated odds-ratio will be derived.

### 7.2 Study Conduct

#### 7.2.1 Accrual

The accrual pattern will be summarized per region, country, investigational site and per month for all enrolled subjects. No separate outputs are provided for N+I vs. CT and for N+C vs. CT. Randomization date, first dosing date, country, investigational site will be presented in a by subject listing of accrual.

#### 7.2.2 Relevant Deviations

The relevant Protocol Deviations will be summarized for all randomized subjects and for all PD-L1 expressing subjects, by treatment group and overall. The following programmable deviations from inclusion and exclusion criteria will be considered as relevant protocol deviations. Non-programmable relevant eligibility and on-treatment protocol deviations, as well as important (both programmable and nonprogrammable) eligibility and on-treatment protocol deviations will be reported via the Clinical Monitoring system (i.e. clinSIGHT).

#### At Entrance

- Subjects without squamous cell carcinoma or adenosquamous cell carcinoma of esophagus
- Subjects with no unresectable advanced, recurrent or metastatic ESCC
- Subjects who have received prior systemic therapy for advanced or metastatic disease (adjuvant, neoadjuvant, and definitive is allowed)
- Subject with baseline ECOG performance status > 1.
- Subjects without any measurable disease at baseline.

• Subjects without any tumor cell PD-L1 result. ("Indeterminate" is not a deviation.)

#### On-treatment

- Subjects receiving concurrent anti-cancer therapy (chemotherapy, hormonal therapy, immunotherapy, curative surgery, non-palliative radiation therapy, standard or investigational agents for treatment of gastric cancer).
- Subjects treated differently as randomized (subjects who received the wrong treatment, excluding the never treated).

A subject listing will also be produced.

## 7.3 Study Population

# 7.3.1 Subject Disposition

The total number of subjects enrolled (randomized or not randomized) will be presented along with the reason for not being randomized.

Number of subjects randomized but not treated along with the reason will be tabulated by treatment group as randomized. This analysis will be performed on all randomized subjects and on all PD-L1 expressing subjects.

Number of subjects who discontinued study treatment along with corresponding reason will be tabulated by treatment group as treated. This analysis will be performed on all treated subjects and on treated PD-L1 expressing subjects.

A subject listing for all randomized subjects will be provided showing the subject's randomization date, first and last dosing date, off study date and reason for going off-study. A subject listing for subjects not randomized will also be provided, showing the subject's race, gender, age, consent date and reason for not being randomized.

# 7.3.2 Demographics and Other Baseline Characteristics

The following baseline characteristics will be summarized by treatment arm as randomized. All baseline presentations identify subjects with missing measurements. This analysis will be performed on all randomized subjects and on PD-L1 expressing subjects. Listings will also be provided.

- Age (descriptive statistics)
- Age category ( $< 65, \ge 65 \text{ and } < 75, \ge 75 \text{ and } < 85, \ge 85; \ge 75, \ge 65$ )
- Gender (male, female)
- Race (White, Black or African American, Asian Indian, Chinese, Japanese, Asian Other, American Indian or Alaska Native, Native Hawaiian or Other Pacific Islander, Other)
- Region (J/K/T, Rest of Asia, RoW) (*stratification factor*)
- Region (Asia, Non-Asia)
- ECOG PS (stratification factor)

- Weight (descriptive statistics)
- Disease stage at initial diagnosis (Stage IA, Stage IB, Stage IIA, Stage IIIB, Stage IIIB, Stage IIIC, Stage IV)
- Histologic grade at initial diagnosis (Gx, G1, G2, G3, G4, unknown)
- Histological classification at initial diagnosis (squamous cell carcinoma, adenosquamous cell carcinoma, other)
- Location at initial diagnosis (upper thoracic, middle thoracic, lower thoracic, gastroesophageal junction)
- TNM classification at initial diagnosis:
  - Tumor (Tx, T0, Tis, T1, T2, T3, T4, unknown)
  - Nodes (Nx, N0, N1, N2, N3, unknown)
  - Metastasis (Mx, M0, M1, unknown)
- Disease status at current diagnosis (recurrent loco-regional, recurrent distant, de-novo metastatic\*\*, unresectable advanced)
- Smoking status (current/former, never smoker, unknown)
- Alcohol use (current/former, never, unknown)
- All lesions at Baseline (Investigator and BICR): sites of disease, number of disease sites per subject, number of subjects with no measurable lesion, number of organs with metastases
- Target Lesions (Investigator and BICR): Presence of target lesions, site of target lesion, sum of diameters of target lesions
- Time from Initial Disease Diagnosis to Randomization (< 6months, 6months < 1 year, 1 < 2 year, 2 < 3 year, 3 < 4 year, 4 < 5 year, ≥ 5 year)
- Time from randomization to first dose date (≤ 3days, 4 5days, 6 7days, 8 14days, 15 21days, >21days, Not Reported or Not Treated)

For the purposes of baseline characteristic summary, stratification factors will be retrieved from the CRF.

\*\* The 'de-novo metastatic' implies cancer which is already metastatic (Stage IV) at first presentation.

#### 7.3.3 Medical History

General medical history will be listed by subject and pretreatment events will be tabulated. This analysis will be performed on all randomized subjects and on PD-L1 expressing subjects.

## 7.3.4 Prior Therapy Agent

Prior therapy will be summarized for all randomized subjects and on all PD-L1 expressing subjects.

#### **Prior anti-cancer therapy:**

• Setting of prior systemic therapy regimen received (adjuvant, neo-adjuvant, definitive CRT).

- Time from completion of prior adjuvant/neo-adjuvant/definitive therapy to treatment (for subjects who received prior adjuvant/neo-adjuvant therapy), (< 6 months, 6 < 12month, ≥ 12 months)
- Prior surgery related to current cancer (yes or no).
  - type of surgery
- Prior radiotherapy (yes or no).
- Prior systemic therapy classified by therapeutic class and generic name.

#### **Other Prior therapy:**

• Prior/current non-study medication classified by anatomic and therapeutic classes.

Agents and medication will be reported using the generic name. A listing by subject will also be provided.

#### 7.3.5 Baseline Examinations

Subjects with abnormal baseline physical examination will be tabulated for all randomized subjects and on all PD-L1 expressing subjects, by examination criteria and by treatment group.

# 7.3.6 Discrepancies between IRT Stratification Factors and Other Datasets

Summary tables (cross-tabulations) by treatment group for stratification factor (except for region and Number of organs with metastases) will be provided to show any discrepancies between what was reported through IRT vs. other data sources at baseline:

- PD-L1 expression level (≥ 1% vs. < 1% or indeterminate) (IRT vs. clinical database)
- ECOG performance status (0 vs. 1) (IRT vs. CRF)

This analysis will be performed on all randomized subjects and on all PD-L1 expressing subjects.

## 7.4 Extent of Exposure

Analyses in this section will be performed in all treated subjects and in treated PD-L1 expressing subjects, by treatment group as treated.

## 7.4.1 Administration of Study Therapy

For details on the dosing schedule per protocol, see Section 2.1.

The following parameters will be summarized (descriptive statistics) by treatment group:

- Relative dose intensity (%) using the following categories: < 50%; 50 < 70%; 70 < 90%; 90 < 110%;  $\ge 110\%$ .
- Number of doses/cycles received (summary statistics).
- Cumulative dose
- Duration of treatment

using a KM curve whereby the last dose date will be the event date for those subjects who are off study therapy. Subjects who are still on study therapy will be censored on their last dose date. Median duration of treatment and associated 95% CI will be provided.

A by-subject listing of dosing of study medication (record of study medication, infusion details, dose change) and a listing of batch number will be also provided.

Key parameters used to characterize dosing data for the N+I arm are defined in Table 7.4.1-1; for the N+C and CT arms, in Table 7.4.1-2.

Table 7.4.1-1: Administration of Study Therapy in the N+I Arm - Definition of Parameters

	Nivolumab	Ipilimumab
Dosing schedule per protocol	3mg/kg Q2WK, IV	1mg/kg Q6WK, IV
Dose*	Total dose administered (mg)/most recent weight (kg)	Total dose administered (mg)/most recent weight (kg)
Cumulative Dose	The sum of all doses (mg/kg) administered to a subject during the treatment period	The sum of all doses (mg/kg) administered to a subject during the treatment period
Relative Dose Intensity (%)	Cum dose (mg/kg) / [(Last nivolumab dose date – nivolumab Start dose date + 14) x 3 / 14 x 100]  Cum dose (mg/kg) / [(Last ipilimumab dose date – ipilimum Start dose date + 42) x 1 / 42 x 100]	
Duration of Treatment	Last dose date (of the last administered study therapy) - Start dose date (of the first administered study therapy) + 1	

\* Dose administered in mg at each dosing date and weight are collected on the CRF

Table 7.4.1-2: Administration of Study Therapy in the N+C and CT Arms

	Nivolumab	Fluorouracil	Cisplatin
Dosing schedule per protocol	240mg Q2WK, IV	800mg/m2/day, Q4WK continuous infusion on Day1-5 of the cycle	80mg/m2 Q4WK, IV
Dose*	Ratio of Total Volume Infused with Total Volume Prepared x 240 in mg	Total dose administered (mg) / most recent BSA	Total dose administered (mg) / most recent BSA
Cumulative Dose	The sum of all doses (mg) administered to a subject during the treatment period	The sum of all doses (mg/m2) administered to a subject during the treatment period	The sum of all doses (mg/m2) administered to a subject during the treatment period
Relative Dose Intensity (%)	Cumulative dose (mg) / [Last nivolumab dose date – nivolumab Start dose date + 14) x 240 / 14]	Cumulative dose (mg/m2) / [First dose of fluorouracil in the last cycle – fluorouracil Start dose date + 28) x 800 x 5 / 28]**	Cumulative dose (mg/m2) / [First dose of cisplatin in the last cycle – cisplatin Start dose date + 28) x 80 / 28]
Duration of Treatment	Last dose date (of the last administered study therapy) - Start dose date (of the first administered study therapy) + 1		

\* Dose administered in mg at each dosing date and BSA (computed using recent weight and baseline height) are collected on the CRF.

\*\* 800 x 5 may be replaced by 1000 x 4 for sites that administer over 4 days.

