### 4.5.1.3 Fluorouracil plus Cisplatin Dosing (Arm C)

Subjects randomized to Arm C will receive treatment with fluorouracil 800 mg/m^2/day as an IV continuous infusion on Day 1 through Day 5 (for 5 days), and cisplatin 80 mg/m^2 as a 30- to 120-minute infusion\* on Day 1 of 4-week cycle. Treatment will continue until progression, unacceptable toxicity, withdrawal of consent, the study ends, whichever occurs first.

\*Subjects are allowed to receive treatment with cisplatin 80 mg/m^2 as an IV infusion over a period of longer than 120 min if it is in accordance with local standard of care/local label.

Doses of fluorouracil and/or cisplatin may be interrupted, delayed, reduced, or discontinued depending on how well the subject tolerates the treatment. See the following [sections](#) for more details: [4.5.2](#) (dose delays) and [4.5.3](#) (dose reductions), [4.5.4](#) (retreatment), and [4.5.5](#) (dose discontinuations).

If either fluorouracil or cisplatin is discontinued the other study treatments may be continued for the remainder of the cycles.

In subjects who required fluorouracil dose reduction due to toxicity during the fluorouracil/cisplatin combination cycles, the dose of fluorouracil may be re-escalated to 800 mg/m^2 after the discontinuation of cisplatin, at the investigator’s discretion and according to local standards, if the prior toxicity was felt to be related mainly to cisplatin.

Subjects should begin study treatment within 3 calendar days of randomization. See Table 4.5.1.3-1 for details on the dosing schedule of fluorouracil plus cisplatin in Arm C.

Dosing calculations of fluorouracil and cisplatin should be based on the body weight assessed at baseline. It is not necessary to re-calculate subsequent doses if the subject weight is within 10% of the weight used to calculate the previous dose. All doses should be rounded up or to the nearest milligram per institutional standard.

Pretreatment hydration for cisplatin can follow local standard of care, or use 1 to 2 liters of fluid (per local standards) infused IV for 8 to 12 hours prior to cisplatin infusion is recommended. Adequate hydration and urinary output must be maintained for at least 24 hours following cisplatin administration. Administration and monitoring should be performed according to local standards. Use of mannitol following the cisplatin infusion should also follow local standards-of-care.

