#### **4.5.8 Treatment of Nivolumab or Ipilimumab Related Infusion Reactions**

Since nivolumab and ipilimumab contains only human immunoglobulin protein sequences, it is unlikely to be immunogenic and induce infusion or hypersensitivity reactions. However, if such a reaction were to occur, it might manifest with fever, chills, rigors, headache, rash, pruritus, arthralgias, hypotension, hypertension, bronchospasm, or other allergic-like reactions. All Grade 3 or 4 infusion reactions should be reported within 24 hours to the study medical monitor and reported as an SAE if it meets the criteria. Infusion reactions should be graded according to NCI CTCAE version 4 guidelines.

Treatment recommendations are provided below and may be modified based on local treatment standards and guidelines, as appropriate:

For Grade 1 symptoms: (mild reaction; infusion interruption not indicated; intervention not indicated):

- Remain at bedside and monitor subject until recovery from symptoms. The following prophylactic premedications are recommended for future infusions: diphenhydramine 50 mg (or equivalent) and/or acetaminophen/paracetamol 325 to 1000 mg at least 30 minutes before additional nivolumab or ipilimumab administrations.

For Grade 2 symptoms: (moderate reaction required therapy or infusion interruption but responds promptly to symptomatic treatment (eg, antihistamines, non-steroidal anti-inflammatory drugs, narcotics, corticosteroids, bronchodilators, IV fluids); prophylactic medications indicated for ≤ 24 hours):

- Stop the nivolumab or ipilimumab infusion, begin an IV infusion of normal saline, and treat the subject with diphenhydramine 50 mg IV (or equivalent) and/or acetaminophen/paracetamol 325 to 1000 mg; remain at bedside and monitor subject until resolution of symptoms. Corticosteroid and/or bronchodilator therapy may also be administered as appropriate. If the infusion is interrupted, then restart the infusion at 50% of the original infusion rate when symptoms resolve; if no further complications ensue after 30 minutes, the rate may be increased to 100% of the original infusion rate. Monitor subject closely. If symptoms recur, then no further BMS-936558 will be administered at that visit.

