### **5.3.2 On-Treatment Safety Assessments**

While on-study the following local laboratory assessments are to be done within 3 calendar days prior to each nivolumab dose: CBC with differential, LFTs (ALT, AST, total bilirubin, alkaline phosphatase), BUN or serum urea level, creatinine, Ca, Na, K, Cl, phosphate, LDH and glucose

Thyroid function testing (TSH with reflexive fT3 and fT4) is to be done every 6 weeks (every 3 cycles) for subjects receiving nivolumab at 3mg/kg q2w (i.e. Arm A), and every 6 weeks for subjects receiving nivolumab at 240 mg q2w (Arm B). Total T3/T4 are acceptable if free T3/T4 are not available.

On treatment pregnancy tests should be performed as per the schedule in the Time & Events table.

Subjects will be evaluated for safety if they have received any study drug. Toxicity assessments will be continuous during the treatment phase as well as during the first two safety follow-up visits. Once subjects reach the survival follow-up phase, either in-person visits or documented telephone calls/email correspondence to assess the subject's status are acceptable.

Adverse events and laboratory values will be graded according to the NCI-CTCAE version 4.

The start and stop time of the study therapy infusions and any interruptions or infusion rate reductions should be documented.

Physical examinations are to be performed as clinically indicated. If there are any new or worsening clinically significant changes since the last exam, report changes on the appropriate non-serious or serious adverse event page.

On treatment local laboratory assessments are to be completed within 3 calendar days prior to nivolumab dosing.

Additional measures, including non-study required laboratory tests, should be performed as clinically indicated or to comply with local regulations. Laboratory toxicities (eg, suspected drug induced liver enzyme evaluations) will be monitored during the follow-up phase via on site/local labs until all study drug related toxicities resolve, return to baseline, or are deemed irreversible.

If a subject shows pulmonary-related signs (hypoxia, fever) or symptoms (eg, dyspnea, cough, fever) consistent with possible pulmonary adverse events, the subject should be immediately evaluated to rule out pulmonary toxicity, according to the suspected pulmonary toxicity management algorithm in the BMS-936558 (nivolumab) IB.

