#### 7.4.2.3 IV Rate Reductions

In this study, it is not allowed that IV rate is reduced.

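### The SAP's Arm A relative dose intensity formulas put the factor 100 in the denominator, the Arm B and C formulas are on a different scale, and SAP 7.4.2.3 contradicts the protocol on infusion-rate reductions

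*SAP*

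**What the plan says.** **Categories.** SAP 7.4.1 will summarise "Relative dose intensity (%) using the following categories: < 50%; 50 < 70%; 70 < 90%; 90 < 110"%, with a top category from 110% upward.

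**Arm A (SAP Table 7.4.1-1).** The nivolumab denominator contains "nivolumab Start dose date + 14) x 3 / 14 x 100", and the square bracket closes after the 100. The ipilimumab denominator has the same form, with 42 days and 1 mg/kg.

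**Arms B and C (SAP Table 7.4.1-2).** The nivolumab denominator is built on "Start dose date + 14) x 240 / 14", with no factor 100. The fluorouracil and cisplatin formulas are built the same way on a 28-day cycle. All three close a parenthesis that was never opened, and the row is labelled as a percentage. A footnote says that the 800 x 5 in the fluorouracil formula "may be replaced by 1000 x 4 for sites that administer over 4 days". The fluorouracil schedule in protocol 4.5.1.3 is a "continuous infusion on Day 1 through Day 5 (for 5 days"), and protocol 4.5.1.2 gives the same for Arm B.

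**Infusion rate.** SAP 7.4.2.3 consists of one sentence: "In this study, it is not allowed that IV rate is reduced". For a Grade 2 reaction in which the infusion was interrupted, protocol 4.5.8 advises sites to "then restart the infusion at 50% of the original infusion rate when symptoms resolve". Protocol 5.3.2 says that "any interruptions or infusion rate reductions should be documented".

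**The concern.** Relative dose intensity is the usual way for a reader to see whether each regimen was delivered as planned. A formula that returns 0.01 for perfect delivery cannot be sorted into categories that run from under 50% to 110% and over. If both tables were coded literally, Arm A would look almost undosed, and its values could not be set beside those of Arms B and C. The version 4.0 document history records a change to the fluorouracil formula in Table 7.4.1-2, so these defects remain after a recent edit.

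The infusion-rate sentence is a different kind of fault. The SAP denies that an event can happen, while the protocol describes when it should happen and asks for it to be written down. As a result the SAP plans no by-arm summary of it. The study uses 30-minute infusions whose acceptability protocol 1.1.7 argues from other trials, so infusion handling is of some interest here.

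**Working it through.** The documents give no worked value of relative dose intensity, so there is no stated figure to reproduce. The check applies each formula as printed to a subject who receives every planned dose on the planned day, assuming constant weight and body surface area.

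**Arm A, nivolumab 3 mg/kg every 2 weeks, 10 doses.**
- Cumulative dose: 10 x 3 = 30 mg/kg. Last minus start: 9 x 14 = 126 days.
- As printed: 30 / [(126 + 14) x 3 / 14 x 100] = 30 / 3000 = 0.01.
- With 100 in the numerator: 100 x 30 / [(126 + 14) x 3 / 14] = 100 x 30 / 30 = 100%.

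**Arm A, ipilimumab 1 mg/kg every 6 weeks, 4 doses.**
- Cumulative dose: 4 mg/kg. Last minus start: 3 x 42 = 126 days.
- As printed: 4 / [(126 + 42) x 1 / 42 x 100] = 4 / 400 = 0.01.
- Corrected: 100 x 4 / 4 = 100%.

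The number of doses cancels, so on-time dosing of any length gives the same result; this was checked for 1 to 52 nivolumab doses and 1 to 17 ipilimumab doses. Taken literally in a percentage row, the value is 0.01%. Taken as a ratio, it is 1%. Both lie below 50%. Even on the ratio reading, a subject would need 50 times the planned dose to leave that category (50% / 1% = 50).

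**Arms B and C, formulas as printed (missing parenthesis supplied).**
- Nivolumab 240 mg, 10 doses: 2400 / [(126 + 14) x 240 / 14] = 2400 / 2400 = 1.0.
- Fluorouracil, 6 cycles: 6 x 4000 = 24000 mg/m2. Last minus start is 5 x 28 = 140 days, so 24000 / [(140 + 28) x 800 x 5 / 28] = 24000 / 24000 = 1.0.
- Cisplatin, 6 cycles: 480 / [(140 + 28) x 80 / 28] = 480 / 480 = 1.0.

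Read as a ratio, 1.0 is 100% and falls in the category from 90% to under 110%. It falls below 50% only if 1.0 is taken as 1%. For identical compliance the Arm A value is 0.01 / 1.0, one hundredth of the value in the other arms.

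**Four-day fluorouracil footnote.** 1000 x 4 = 4000 mg/m2 and 800 x 5 = 4000 mg/m2 per cycle. The denominator is the same either way, so the footnote changes no relative dose intensity value.

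**Infusion rate, side by side.** SAP 7.4.2.3 says that reductions are not permitted. Protocol 4.5.8 recommends one in a defined situation for nivolumab or ipilimumab, and protocol 5.3.2 asks for reductions to be documented. These statements cannot all describe the same trial.

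**The case against.** **The bracket is an obvious slip.** Every Arm A subject at 0.01 would show in the first test output, and a programmer would correct it. A layout fault in the table is also possible. The first part is likely, but a pre-specified plan should not rely on an unrecorded correction. On the second, the factor sits inside the bracket in two separate formulas.

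**Arms B and C are sound.** This largely stands. A reader might infer that nearly all treated subjects in the trial would land below 50%, and so that the evidence on dosing of the control arm and the Arm B chemotherapy is lost. The documents do not support that: those formulas return the correct ratio, and what they lack is a factor 100 and a parenthesis. The forced misclassification is confined to Arm A.

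**Rate reductions are already covered indirectly.** In protocol 4.5.8 the half-rate restart follows an interruption. SAP 7.4.2.2 summarises interrupted infusions with reasons and number per subject, and SAP 7.4.1 provides a by-subject listing that includes infusion details. The protocol text is a recommendation that local standards may modify, and the rate may return to full after 30 minutes without complications. All of this stands and limits the consequence, but it does not remove the contradiction. It is also not certain that rate reductions are in the database: protocol 5.3.2 asks for them to be documented, yet the same section says that some assessments may not be captured in the eCRF.

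**The fluorouracil footnote.** A reader might infer that it hides protocol deviations and so weakens the 10% trigger for the OS and PFS analysis in subjects without relevant deviations (SAP 7.5.2.2). That does not follow. The footnote concerns only a dose intensity denominator, and the same table still gives Days 1 to 5 as the protocol schedule. SAP 7.2.2 lists programmable deviations and sends non-programmable relevant ones through the clinical monitoring system. The number of 4-day sites is not given.

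**Conclusion.** The point holds in three parts of unequal weight.

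1. Both Arm A formulas are wrong as printed. They give 0.01 for full dosing and put the subject below 50% under either reading. The error is a factor of 100 on the ratio reading and 10,000 on the literal percentage reading (100% / 0.01%). The three Arm B and C formulas are incomplete rather than wrong in substance, but they are on a different scale from Arm A.
2. SAP 7.4.2.3 directly contradicts protocol 4.5.8 and 5.3.2. How many rate reductions occurred, and whether the CRF captures them, cannot be told from the documents.
3. The 4-day footnote has no numerical effect. It names a schedule not found in protocol 4.5.1.2 or 4.5.1.3; 4-day regimens appear in the protocol only as guideline background in 1.1.5.1. The passages need reconciling.

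The effects are limited to descriptive exposure tables. The arithmetic rests on constant weight and body surface area, on on-time dosing, and on the bracket positions as printed.

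**What to change.** - In both tables, write every formula as 100 x cumulative dose / [(last - start + interval) x planned dose per interval / interval], with balanced brackets. For fluorouracil and cisplatin, keep the first dose of the last cycle as the last date. Full dosing then gives 100% in every arm.
- Replace the sentence in SAP 7.4.2.3 with a by-arm summary: subjects with at least one infusion-rate reduction, number per subject, and reason, to the extent that the CRF captures them. Otherwise, refer to the infusion-details listing. Reconcile the section with protocol 4.5.8 and 5.3.2. Summarising whatever was recorded does not require this review to say which clinical rule is right.
- Reconcile the 4-day fluorouracil footnote with protocol 4.5.1.2 and 4.5.1.3. This review does not say which schedule is right.

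The cost is SAP wording and at most one further exposure table. No efficacy analysis has to be revisited.
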